9.2.1.2.2. Cohort 2 (Biologics cohort): Adult UC Patients Treated with Biologics

- 1. Initiation of biologic therapy (i.e. first prescription for a specific TNFi or non-TNFi agent) as captured in Marketscan since 30 May 2018
- 2. Patients with either 1 UC diagnosis code from an inpatient visit or ≥2 of any of the ICD-10 codes for UC in Table 1 from an outpatient visit prior to index date (i.e. date of first prescription for a specific biologic agent; at least one of the two required diagnoses from outpatient visits must be made by a gastrointestinal specialist)

Patients in this cohort will be assessed overall, and independently stratified by TNFi and non-TNFi use. Patients may also be on immunomodulators/immunosuppressants concurrently.

9.2.1.2.3. Cohort 3 (Immunomodulators/immunosuppressants cohort): Adult UC Patients Treated with Immunomodulators/Immunosuppressants without concurrent Biologics

- 1. Initiation of immunomodulator/immunosuppressant therapy (i.e. first prescription for a specific immunomodulator/immunosuppressant agent) as captured in Marketscan since 30 May 2018 (without concurrent biologics)
- 2. Patients with either 1 UC diagnosis code from an inpatient visit or ≥2 of any of the ICD-10 codes for UC in Table 1 from an outpatient visit prior to index date (i.e. date of first prescription for an immunomodulator/immunosuppressant agent; at least one of the two required diagnoses from outpatient visits must be made by a gastrointestinal specialist)

9.2.1.2.4. Cohort 4 (Naive cohort): Biologic/immunomodulator/immunosuppressantnaïve Cohort

- 1. Naive to biologics/immunomodulators/immunosuppressants using all available data
- 2. Patients with either 1 UC diagnosis code from an inpatient visit or ≥2 of any of the ICD-10 codes for UC in Table 1 before start of follow-up (at least one of the two required diagnoses from outpatient visits must be made by a gastrointestinal

specialist). For these patients, start of follow-up will be defined by an index date as described in Section 9.3.4.2.

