- Surgery for UC
- Death

For contextualization and risk characterization purposes, the incidence rates of the same safety events (listed in the primary and secondary objectives above) in adult UC patients initiating treatment with other approved systemic agents, as well as those patients naïve to biologics and immunomodulators/immunosuppressants will also be assessed. Therefore in total, incidence rates will be estimated within the following groups:

1. Cohort 1 (Tofacitinib cohort): UC patients initiating tofacitinib, overall and independently stratified by dose (5 mg twice daily, 11 mg once daily, 10 mg twice daily, 22 mg once daily) and prior biologic use (i.e. patients naïve to biologics vs. patients with prior biologic use)

Contextualization Cohorts:

- 2. Cohort 2 (Biologics cohort): UC patients who initiate biologics, with/without concurrent immunomodulators/immunosuppressants, overall and independently stratified by TNFi/non-TNFi use and number of previous biologic treatments
- 3. Cohort 3 (Immunomodulators/immunosuppressants cohort): UC patients who initiate immunomodulators/immunosuppressants (methotrexate [MTX], azathioprine [AZA], mercaptopurine [6-MP]) without concurrent biologics
- 4. Cohort 4 (Naïve cohort): UC patients naïve to both biologics and immunomodulators/immunosuppressants

Patients in the naïve cohort are expected to have milder disease relative to patients in the other 3 cohorts.

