9.2.1.1. Drug Utilization Study

To assess utilization patterns of tofacitinib use, all patients enrolled in the Marketscan database during the study observation period (i.e. from time of first US approval for tofacitinib in 2012 through to end of data collection in 2025) who have received ≥ 1 prescription of tofacitinib will be included.

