9.2.1.2. Active surveillance study

The active surveillance population to be used for the estimation of the incidence rates of the safety events of interest will be a subset of the population described above, and will include all adult UC patients aged ≥18 years who are enrolled in the Marketscan database from the time of approval of tofacitinib for UC in the US (May 2018) through to the end of data collection (June 2025) for the study. UC patients will be identified via ICD-10 codes listed in Table 1. Using all available data, UC patients must have at least one UC diagnosis code from an inpatient visit, or at least two occurrences of a UC diagnosis code from outpatient vists, with at least one of the two outpatient codes documented by a gastrointestinal specialist. UC codes assigned on different dates do not need to be the same to qualify. At least 12 months of continuous (i.e., no more than a 30-day gap) database enrollment before index date is required to enable analysis of baseline patient and disease characteristics that may be important modifiers of the relationship of UC with safety endpoints of interest. Index date is defined in the treatment cohort inclusion criteria listed in the subsections below.

ICD-9 Code	Diagnosis	ICD-10 code	Diagnosis
556 (no 3 rd digit)	Ulcerative colitis		
556.0	Ulcerative enterocolitis	K51.8 (all billable codes under K51.8)	Other UC
556.1	Ulcerative ileocolitis	K51.8 (all billable codes under K51.8)	Other UC
556.2	Ulcerative proctitis	K51.2 (all billable codes under K51.2)	Ulcerative (Chronic) Proctitis
556.3	Ulcerative proctosigmoiditis	K51.3 (all billable codes under K51.3)	Ulcerative (Chronic) Rectosigmoiditis
556.5	Left-sided ulcerative colitis	K51.5 (all billable codes under K51.5)	Left Sided Colitis
556.6	556.6 Universal ulcerative colitis		Ulcerative (Chronic) Pancolitis
556.8	Other ulcerative colitis	K51.8 (all billable codes under K51.8)	Other Ulcerative Colitis
556.9	Ulcerative colitis, unspecified	K51.9 (all billable codes under K51.9)	Ulcerative Colitis, Unspecified

Table 1. ICD Codes for UC Diagnoses within MarketScan Database

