Patients may switch between the tofacitinib and contextualization cohorts over time if inclusion/exclusion criteria listed below are met. Additionally, patients will be eligible for entry into a particular cohort each time they start a new therapy within the same drug class. For acute endpoints, patients will be censored from a particular cohort when they start a new therapy in a different drug class. For the endpoint of MACE, for example, patients in Cohort 1 (UC patients initiating treatment with tofacitinib) will be censored if and when they switch to a specific biologic agent, but will be eligible for subsequent inclusion into Cohort 2 (patients initiating treatment with biologics). For non-acute outcomes such as malignancy and death, outcomes will be evaluated using a "once exposed always at risk" paradigm (as described in Section 9.3.5).

Formal definitions of index dates/start of follow-up are provided in Sections 9.3.4.2 and 9.3.5.Details of exposure measurement (e.g., allowing specified gaps between prescriptions in continuous exposure, etc.) will be detailed in the statistical analysis plan (SAP).

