9.2.2. Exclusion Criteria

To assess to facitinib utilization patterns, no exclusion criteria will be applied. However, for the active surveillance population which will consist of a subset of the study population, patients not meeting the inclusion criteria for any of the respective cohorts described above will be excluded.

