In the above scenario, the patient has two biologic initiations and a tofacitinib initiation. The initiation of tofacitinib therapy occurs within the 90-day extension period for the first biologic. Thus, the time and event during the overlapping period will be assigned to both the first biologic and tofacitinib. Specifically, for the first biologic initiation, a safety event occurred within the 90-day extension period, and exposure time is counted from the time of drug initiation (Index date 1) until the occurrence of the safety event. For the tofacitinib initiation, one safety event occurred and exposure time is counted from Index date 2 (date of initiation of tofacitinib which occurs within the 90-day extension period of the first biologic initiation) to the occurrence of the safety event (which also occurred within the 90-day extension period for the first biologic). Tofacitinib treatment was discontinued when the safety event occurred, and there is a period of time where no treatment is used. For the second biologic initiation, one safety event occurred and exposure time is counted from Index date 3 to the safety event.

For the purpose of analysis, the patient has 2 biologic initiations and a tofacitinib initiation:

A sensitivity analysis whereby if a new medication is started during the 90-day window after discontinuation of a previous medication, initiation of the new medication will stop the 90-day risk window, and any event prior to the new medication start will be assigned to the discontinued medication will also be conducted and further discussed in the SAP. The 90-day extension period is implemented in part to accommodate ongoing exposure to treatments with longer half-lives, and in part to ensure that any subclinical or undiagnosed illness at time of end of treatment is captured. For each patient, follow-up time contributing to one of the three treated cohorts will be calculated as the sum of dispensed medication days (based on days supply) plus the 90-day extension period.

For NMSC and malignancies, surgery for UC, and death (and as a sensitivity analysis for PML), the occurrences of which are expected to be delayed relative to the time of exposure, the outcomes will be evaluated from drug initiation until the first event or loss to follow up, reflecting a "once-exposed always at risk" paradigm. If a patient switches to a new drug, the subsequent observation time will contribute to multiple therapies.

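### As written, Cohort 4 (naive) is kept free neither of tofacitinib nor of later treated time, and the source population of Cohorts 2 to 4 is stated inconsistently

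*Protocol*

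**What the plan says.** **Eligibility.** Section 9.2.1.2.4 requires Cohort 4 patients to be "Naive to biologics/immunomodulators/immunosuppressants using all available data" and to meet the UC diagnosis rule. Section 8, in defining Cohort 3, spells out the second drug group as "immunomodulators/immunosuppressants (methotrexate [MTX], azathioprine [AZA], mercaptopurine [6-MP]) without concurrent biologics". Tofacitinib is not in that list and forms its own cohort. Section 9.2.2 adds no exclusion for tofacitinib.

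**Source population.** Section 9.2.1.1 defines the drug utilization population by use of the drug: all enrolled patients with at least one "prescription of tofacitinib will be included". Section 9.2.1.2 then says that the active surveillance population "will be a subset of the population described above, and will include all adult UC patients aged ≥18 years" enrolled in the database from May 2018. Section 9.2.2 repeats the idea: "active surveillance population which will consist of a subset of the study population". The abstract (Section 4) instead describes the contextualization cohorts as additional to the tofacitinib sub-population.

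**Follow-up.** Section 9.2.1.2 states censoring at the start of a different drug class for acute endpoints. For NMSC and malignancies, surgery for UC and death, Section 9.3.5 says that "the outcomes will be evaluated from drug initiation until the first event or loss to follow up", and that time after a switch counts under more than one therapy. Under Section 9.3.4.2 the Cohort 4 index date is the UC diagnosis date, not a drug start.

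**The concern.** Cohort 4 is the only group without biologic or immunomodulator treatment against which the tofacitinib malignancy rate can be read. It can do that job only if its patients and its person-time are untreated. Three pieces of wording work against this: tofacitinib is missing from the naivety criterion, the subset sentence points to tofacitinib users as the source, and no rule ends naive follow-up for delayed outcomes when treatment starts. If the treated rate is higher, treated time counted as naive raises the naive rate and pulls the contrast with the treated cohorts toward no difference. In a safety study that is the unhelpful direction.

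**Working it through.** The protocol gives no figure on this point, so there is none to reproduce. The check is a reading of the rules followed by an illustration.

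**1. Can a tofacitinib user enter Cohort 4?** Yes. Such a patient breaches neither part of the naivety criterion. Section 9.2.1.2.1 also treats potent immunosuppressants as drugs that might be taken alongside tofacitinib, that is, as distinct from it. Nor is the case hypothetical: Section 8 stratifies Cohort 1 into biologic-naive and biologic-experienced patients, and makes the proportion of TNFi-naive UC patients on tofacitinib an objective. Section 9.7.1 classes such use before 01 July 2019 as on-label, and that period falls at the start of the surveillance window.

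**2. Where are Cohorts 2 to 4 drawn from?** Two readings stand in one sentence of Section 9.2.1.2. The first half ("will be a subset of the population described above") limits them to patients with at least one tofacitinib prescription. The second half takes all adult UC enrollees. Taken literally, the first half makes 100% of Cohorts 2 to 4 ever-users of tofacitinib. The preliminary counts in Section 9.5 (2016–2018) give a crude ceiling for such a pool: 11,857 / 59,080 = 20.1% of UC patients, even if every tofacitinib user had UC. The 11,857 covers all indications.

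**3. When does Cohort 4 follow-up end for malignancy?** No rule is written for Cohort 4 itself. Censoring at a new class is stated for acute endpoints. The delayed-outcome rule runs to first event or loss to follow-up and presupposes a drug start. The person-time formula in Section 9.3.5 covers only the three treated cohorts. Applied to Cohort 4, the general rule leaves time after a first systemic therapy in the naive denominator and events after it in the naive numerator.

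**4. Illustrative size.** All inputs are assumptions; none is in the protocol. Let each patient have 4 years of follow-up, let a share p start any systemic therapy at year 1, and let the treated rate be RR times the untreated rate.

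- Treated share of naive person-time: s = p × (4 − 1) / 4
- Naive rate relative to the truly untreated rate: (1 − s) + s × RR = 1 + s × (RR − 1)

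| p | s | RR = 1.5 | RR = 2 |
|---|---|---|---|
| 10% | 7.5% | 1.0375 | 1.075 |
| 20% | 15% | 1.075 | 1.15 |
| 30% | 22.5% | 1.1125 | 1.225 |

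The naive rate is about 4–11% too high at RR 1.5 and 8–23% too high at RR 2. A true treated-to-naive ratio of 2 would appear as 2/1.075 = 1.86 down to 2/1.225 = 1.63.

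The formula applies the raised rate from the first treated day. If it appears only after one year of treatment, s becomes p × 2/4, or 5–15%. The inflation is then 2.5% (p = 10%, RR 1.5) to 15% (p = 30%, RR 2).

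**5. Tofacitinib alone.** If time after tofacitinib start were 1–5% of naive person-time (assumed) and RR were 2, the naive rate would be 1.01 to 1.05 times the untreated rate.

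**The case against.** The strongest reply is that the intended design is clear and the real contamination small. Much of this stands.

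- **Source population.** A reader might infer from the subset sentence that Cohorts 2 to 4 consist wholly of tofacitinib users and are unusable. The documents do not support that as the design. The same sentence takes all adult UC enrollees, the abstract adds the other cohorts, Section 9.5 counts UC patients without requiring tofacitinib, and Section 8 expects the naive cohort to have milder disease. It is a contradiction to reconcile.
- **Immortal time.** A reader might also infer that Cohorts 2 and 3 would hold only patients who survived and stayed enrolled until they received tofacitinib. Even the literal wording does not require this, because a patient who took tofacitinib first and a biologic later also qualifies. Section 9.2.1.2 uses that sequence as its example.
- **Selection on the future.** The reference to all available data in the naivety criterion could be read as never treated at any time. Unlimited look-back is the more natural reading: Sections 9.3.1 and 9.3.2 use the same phrase for prior TNFi use. The criterion should still say so.
- **Tofacitinib's share.** Section 9.2.1.2.1 does not expect tofacitinib in newly diagnosed UC, and Section 7 describes the July 2019 label change to patients with TNFi failure or intolerance. Prior TNFi or methotrexate use disqualifies from Cohort 4. The share is therefore probably small, but the table in the working concerns any systemic therapy.
- **Follow-up.** Section 9.3.5 opens with a general rule that lists a treatment switch among the ends of follow-up. That the malignancy rule continues past treatment start in Cohort 4 is inferred from the delayed-outcome rule, not stated for that cohort. The statistical analysis plan, not seen here, may define it.

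The last reply does not dispose of the point. Section 9.2.1.2 leaves exposure measurement to the statistical analysis plan, but the protocol itself fixes the eligibility criteria, the source population and the delayed-outcome rule.

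**Conclusion.** The point holds in a limited form. As written, Cohort 4 does not bar tofacitinib, the source of Cohorts 2 to 4 is stated inconsistently, and the only rule for delayed outcomes does not fit a cohort without a drug start and would leave treated time in the naive rate.

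The size is unknown. Under the assumed inputs the naive rate would be up to about 4–23% too high, and less if the effect on malignancy is delayed.

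A reader might infer that the primary result is compromised. It is not: the primary objective is the malignancy rate in Cohort 1, the study is descriptive without a priori hypotheses, and Cohort 4 serves contextualization only. This should be fixed for the sake of the contextualization rates.

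**What to change.** 1. Delete or correct the subset wording in Sections 9.2.1.2 and 9.2.2, so that Cohorts 2 to 4 come from all eligible adult UC enrollees.
2. In Section 9.2.1.2.4, define Cohort 4 as having no claim for tofacitinib, a biologic or an immunomodulator/immunosuppressant in all data up to and including the index date.
3. In Section 9.3.5, give Cohort 4 its own follow-up rule: person-time ends at the first such claim for every outcome, including malignancy, NMSC, surgery for UC and death.
4. Report uncensored Cohort 4 follow-up as a sensitivity analysis, because starting therapy is likely to track worsening disease and censoring there may be informative.

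The cost is amendment wording and one censoring flag built from claims already in the database. The price in the data is somewhat shorter naive follow-up and possible informative censoring, which item 4 helps to gauge.

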9.2.2. Exclusion Criteria

To assess to facitinib utilization patterns, no exclusion criteria will be applied. However, for the active surveillance population which will consist of a subset of the study population, patients not meeting the inclusion criteria for any of the respective cohorts described above will be excluded.

9.3. Variables

A summary of all relevant study variables is provided in the sections below. Detailed definitions, including relevant ICD codes and procedure codes used to define safety events of interest for the active surveillance portion of the study and other variables, will be included in the SAP.

9.3.1. Baseline Data

Baseline data for both the drug utilization and active surveillance components of the study will include the following, as appropriate:

- Age (years) at index date
- Sex (male/female)
- Age of UC onset (years)/years since UC diagnosis (i.e. from date of first inpatient UC diagnosis code or second outpatient UC diagnosis code to index date)
- Smoking status (yes/no as per algorithm based on diagnosis and procedure codes²⁴)
- Comorbidities (within 12 months of index date for non-malignancy events, and ever for malignancy events) e.g.
 - o history of malignancies,
 - o history of serious infection,
 - o history of opportunistic infection,
 - o history of herpes zoster,
 - history of venous thromboembolism,
 - history diabetes mellitus,
 - o history of myocardial infarction [MI],
 - history of heart failure

- o history of hypertension,
- history of inherited coagulation disorders
- Prior TNFi use (using all available data)
- Concomitant use of immunomodulators/immunosuppressants at index date
- Use of the following medications within 12 months of index date:
 - o oral contraceptives or hormonal therapy
 - o oral steroids,
 - o oral nonsteroidal anti-inflammatory drugs [NSAIDs],
 - o antimicrobials,
 - o anticoagulants,
 - o beta blockers,
 - o bisphosphonates,
 - o narcotics,
 - proton pump inhibitors [PPIs]
 - statins

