9.3.4.2. Active Surveillance Study

For the active surveillance portion of the study, index date will be defined as follows:

Cohort 1: This will be the date of first prescription for tofacitinib since 30 May 2018, following a diagnosis of UC as described in Section 9.2.1.2.1.

Cohort 2: This will be the date of first prescription for a specific biologic agent since 30 May 2018, following diagnosis of UC as described in Section 9.2.1.2.2. For patients with more than one biologic initiation, more than one index date will be defined (e.g., one for each biologic initiation).

Cohort 3: This will be the date of first prescription for a specific immunomodulator/immunosuppressant agent since 30 May 2018, following diagnosis of UC as described in Section 9.2.1.2.3. For patients with more than one immunomodulator/immunosuppressant initiation, more than one index date will be defined.

Cohort 4: This will be the date of UC diagnosis as described in Section 9.2.1.2.4, since 30 May 2018.

[figure not shown]

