In addition, due to limitations related to the database, all-cause mortality cannot be assessed since only in-hospital deaths are captured. This may result in an underestimation of the outcome as deaths occurring in other environments (e.g. home, institutions, etc.,) cannot be captured. Additionally, due to privacy concerns, in-hospital deaths cannot be directly captured in the database, and must be estimated via use of an algorithm which will developed as part of this study and will not be able to be validated for use in claims databases. As such, in-hospital deaths may not be accurately captured in this study. For acute events, a 90 day extension period is implemented in part to accommodate ongoing exposure to treatments with longer half lives, and in part to ensure that any subclinical or undiagnosed illness at time of end of treatment is captured. However, there is the possibility of potential misclassification of the exposure window for any treatments for which the half-life is shorter, leading to a potential underestimation of incidence rates for some outcomes.

As tofacitinib is a new UC medication, it is possible that patients treated with it will represent those with the most severe cases of disease, longer disease duration, history of multiple failed

UC therapies and physical comorbidities that place patients at risk for events. Channeling may present as increased rates of safety events of interest in the early phases of the study. Incidence rates from the contexualization cohorts may illuminate such channeling via stratification on key indicators of disease severity such as number of previous biologic treatments, patient characteristics and past therapies. However, certain patient characteristics which may influence VTE risk (e.g. obesity and immobilization), cannot be reliably captured, and thus may limit data interpretation. Trend analyses may be conducted to evaluate rates in tofacitinib patients over time. Analysis may be unable to identify or control for any changes in rates due to changes in the treatment landscape.

Conclusions from this study may be limited to the duration of treatment captured. Finally, while these data may be generalizable to the commercially insured population and patients on Medicare, they may not be representative of those whose primary insurance is through Medicaid.

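### Years since UC diagnosis and age at UC onset run from the first qualifying codes in the database: a lower bound on duration for patients diagnosed before entry, and 0 in Cohort 4 on the plain reading

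*Protocol*

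**What the plan says.** Section 9.3.1 lists age of UC onset and disease duration as one baseline item, with duration defined as "years since UC diagnosis (i.e. from date of first inpatient UC diagnosis code or second outpatient UC diagnosis code to index date". The list serves both the drug utilization and the active surveillance components.

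Section 9.2.1.2 sets how far back the codes are sought and how much history is guaranteed:
- "Using all available data, UC patients must have at least one UC diagnosis code from an inpatient visit", or two outpatient codes, "with at least one of the two outpatient codes documented by a gastrointestinal specialist".
- "At least 12 months of continuous (i.e., no more than a 30-day gap) database enrollment before index date is required".

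In Cohorts 1–3 the index date (Section 9.3.4.2) is a first prescription after the UC diagnosis. For Cohort 4 the same section says: "This will be the date of UC diagnosis as described in Section 9.2.1.2.4, since 30 May 2018". Section 9.2.1.2.4 asks for "Patients with either 1 UC diagnosis code from an inpatient visit or ≥2 of any of the ICD-10 codes for UC in Table 1 before" the start of follow-up, and adds: "For these patients, start of follow-up will be defined by an index date as described in Section 9.3.4.2".

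Section 9.9 warns that tofacitinib patients may be "those with the most severe cases of disease, longer disease duration, history of multiple failed" therapies, and that this may raise their event rates. It does not mention that recorded duration is cut off at database entry or that it has no spread in Cohort 4.

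**The concern.** UC is chronic, and Section 9.2.1.2.1 does not expect tofacitinib to be given to newly diagnosed patients. Many Cohort 1 patients may therefore have been diagnosed before they entered the database. For them the stated rule counts only the part of the disease course that falls inside the observable claims history.

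In Cohort 4 the start of the clock and the index date appear to be the same event, so the variable would carry no information there.

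At stake is the baseline description. A reader who wants to see whether tofacitinib patients had longer disease, as Section 9.9 suggests, would look at this row. Durations in the treated cohorts would be compressed, onset ages shifted upwards, and the contrast with Cohort 4 set mainly by the definitions.

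**Working it through.** The plan states no figure for this variable, so there is none to reproduce. The check is date arithmetic on the definitions, plus an illustration with assumed inputs.

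**1. Cohorts 1–3.** Let D be true time from diagnosis to index, E the observable history before index, and g the delay from the later of diagnosis and database entry to the qualifying code. Then

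recorded duration R = max(min(D, E) − g, 0), and recorded onset age = age at index − R, which is too old by D − R.

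- Diagnosed while observable (D ≤ E): R is D − g, so the error is only the coding delay.
- Diagnosed before entry (D > E): R cannot exceed E. For example, with D = 15 years and E = 14 months (1.17 years), R is at most 1.17 years and the onset age is at least 15 − 1.17 = 13.83 years too old.

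The share with D > E depends on two distributions that the documents do not give. As an illustration, assume D exponential with mean m, E = 1 year plus an exponential with mean e, and g uniform on 0–0.5 year (400,000 draws per row):

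| m (y) | e (y) | share with D > E | mean true D (y) | mean recorded R (y) | mean onset-age error (y) |
|---|---|---|---|---|---|
| 4 | 1 | 62% | 3.99 | 1.27 | 2.72 |
| 4 | 3 | 44% | 4.00 | 1.98 | 2.02 |
| 4 | 6 | 31% | 4.01 | 2.52 | 1.49 |
| 8 | 1 | 78% | 8.01 | 1.48 | 6.53 |
| 8 | 3 | 64% | 8.01 | 2.62 | 5.39 |
| 8 | 6 | 51% | 8.01 | 3.72 | 4.29 |
| 12 | 1 | 85% | 11.98 | 1.56 | 10.42 |
| 12 | 3 | 74% | 12.01 | 2.92 | 9.09 |
| 12 | 6 | 61% | 11.96 | 4.40 | 7.56 |

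The share can be checked by hand: P(D > E) = exp(−1/m) × m/(m + e). For m = 4, e = 6 this is 0.779 × 0.40 = 0.31; for m = 12, e = 1 it is 0.920 × 0.923 = 0.85.

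A second set of assumptions (median D of 5, 8 or 12 years; e of 1, 2 or 4 years; no coding delay) gives 56% to 89% truncated and recorded medians of 1.49 to 3.07 years.

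In the first set the correlation of R with true duration is 0.18 to 0.69, and with E it is 0.31 to 0.80. R therefore mixes the two.

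**2. Cohort 4.** Here R = index date − diagnosis date.

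- Plain reading, with the index on the day the qualifying diagnosis is completed (e.g. second outpatient code, by a specialist, on 1 March 2020): R = 0, and onset age equals age at index.
- The specialist condition is in the cohort criterion but not in the Section 9.3.1 definition. With a second outpatient code on 1 March 2019 and the first specialist code, taken as index, on 1 September 2019: R = 184/365.25 = 0.50 year.
- The May 2018 limit does not say how patients coded earlier are handled. If the index is their first qualifying diagnosis after that date, then with a diagnosis on 1 June 2015 and an index on 1 July 2018: R = 1,126/365.25 = 3.08 years.

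The zero is thus the plain reading, with exceptions where the wording is open. Asking for the codes before follow-up starts, while starting follow-up on the diagnosis date, adds to that uncertainty.

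**The case against.** A reader might infer that the variable simply records time enrolled. The documents do not support that. Cohort 4 must have at least 12 months of enrolment before index, so a measure of enrolment would be at least 1 year there, not 0. A patient first diagnosed while enrolled gets about the right value. For the same reason it would be wrong to say that duration is understated in all treated patients.

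The 12 months are a minimum, not the search window. All available data are used, and Sections 9.2 and 9.4.1 date the database from 1996. Observable history may be long for many patients. This stands, and it is why the percentages above are illustrations only.

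A zero may also be roughly right in Cohort 4, since these patients were enrolled for a year or more before the UC definition was met. This stands in part. No UC-code-free period is required, however, so an earlier single outpatient code is possible and new diagnosis is not established. Even if all were newly diagnosed, the gap from Cohorts 1–3 would still come from indexing one cohort at diagnosis and the others at a later prescription.

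Finally, the consequence is limited. The study is descriptive. Disease duration is not a named stratum in Section 9.7.2 or 9.7.4, and Section 9.9 looks to previous biologics, patient characteristics and past therapies to show channelling. No duration comparison with Cohort 4 is announced, and Section 8 already expects milder disease there. The code-based origin is openly stated, and Section 9.9 gives a general warning about missing clinical detail in claims. All this is correct and confines the point to the baseline table. It does not remove it: the protocol fixes the rule itself, names duration as a channelling factor, and omits this limitation while listing others as specific as the sensitivity of the smoking algorithm.

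**Conclusion.** The point holds for the baseline description. For patients diagnosed before database entry, the Section 9.3.1 variable is a lower bound on disease duration, capped by observable history, and it makes onset age too old. For patients diagnosed while enrolled it is about right. The share affected cannot be taken from the documents; the assumed inputs above give 31% to 89%, a range that shows how far the result depends on the assumptions and is not an estimate.

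On the plain reading of Sections 9.3.1 and 9.3.4.2, recorded duration is 0 for Cohort 4, so a difference from Cohorts 1–3 largely follows from the choice of index date. A reader might take this to bias the safety results. It does not: the crude incidence rates, including the primary malignancy rate, do not use this variable.

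**What to change.** 1. In Section 9.3.1 keep the qualifying-code origin, but label the variable 'time from first recorded qualifying UC diagnosis to index (lower bound)'. Moving the origin to any single first code is not needed, and it would sit badly with the Section 9.9 warning about rule-out coding.
2. Report available look-back length by cohort beside it.
3. Report age at UC onset only in patients with at least 12 months of UC-code-free enrolment before their first UC code.
4. State in Section 9.9 that duration is left-truncated at database entry and is not compared between Cohort 4 and Cohorts 1–3.

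The cost is one reworded variable, one added table row and a short limitation statement. The downside is that onset age is reported for fewer patients.
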